7.2.4 Pharmacology

Sotorasib exposure-response relationships and the time course of the pharmacodynamic response are unknown.

The pharmacokinetics of sotorasib have been characterized in healthy subjects and in patients with KRAS G12C-mutated solid tumors, including NSCLC. Sotorasib exhibited non-linear, time-dependent, pharmacokinetics over the dose range of 180 mg to 960 mg (0.19 to 1 time the approved recommended dosage) once daily with similar systemic exposure (i.e., AUC_{0-24h} and C_{max}) across doses at steady-state. Sotorasib systemic exposure was comparable between film-coated tablets and film-coated tablets predispersed in water administered under fasted conditions. Sotorasib plasma concentrations reached steady state within 22 days. No accumulation was observed after repeat LUMAKRAS dosages with a mean accumulation ratio of 0.56 (coefficient of variation (CV): 59%).

Absorption:

The median time to sotorasib peak plasma concentration is 1 hour.

Effect of Food:

When 960 mg LUMAKRAS was administered with a high-fat, high-calorie meal (containing approximately 800 to 1000 calories with 150, 250, and 500 to 600 calories from protein, carbohydrate and fat, respectively) in patients, sotorasib AUC_{0-24h} increased by 25% compared to administration under fasted conditions.

Distribution:

The sotorasib mean volume of distribution (Vd) at steady state is 211 L (CV: 135%). In vitro, sotorasib plasma protein binding is 89%.

Elimination:

The sotorasib mean terminal elimination half-life is 5 hours (standard deviation (SD): 2). At 960 mg LUMAKRAS once daily, the sotorasib steady state apparent clearance is 26.2 L/hr (CV: 76%).

Metabolism:

The main metabolic pathways of sotorasib are non-enzymatic conjugation and oxidative metabolism with CYP3As.

Excretion:

After a single dose of radiolabeled sotorasib, 74% of the dose was recovered in feces (53% unchanged) and 6% (1% unchanged) in urine.

Specific Populations:

No clinically meaningful differences in the pharmacokinetics of sotorasib were observed based on age (28 to 86 years), sex, race (White, Black and Asian), body weight (36.8 to 157.9 kg), line of therapy, ECOG PS (0, 1), mild and moderate renal impairment (eGFR: ≥ 30 mL/min/1.73 m²), or mild hepatic impairment (AST or ALT $< 2.5 \times$ ULN or total bilirubin $< 1.5 \times$ ULN). The effect of severe renal impairment or moderate to severe hepatic impairment on sotorasib pharmacokinetics has not been studied.

7.2.5 Supplier

Amgen Pharmaceuticals

7.2.6 Sotorasib Dosage and Administration

The recommended dosage of sotorasib is 960 mg (eight 120 mg tablets) orally once daily until disease progression or unacceptable toxicity. Take sotorasib at the same time each day with or without food. Swallow tablets whole. Do not chew, crush or split tablets. On the days of Tarloxotinib infusion, Sotorasib should be taken at the same time as the start of the infusion.

7.2.7 Missed Doses

If a dose of sotorasib is missed by more than 6 hours, take the next dose as prescribed the next day. Do not take 2 doses at the same time to make up for the missed dose. If vomiting occurs after taking sotorasib, do not take an additional dose. Take the next dose as prescribed the next day.

7.2.8 Dose Modifications for Adverse Reactions

Dose level -1	480mg once daily
Dose level -2	240mg once daily

Sotorasib should be discontinued if further dose reduction is indicated below 240mg once daily.

Adverse reaction	Dosage modification
Grade 2 AST or ALT elevation with symptoms Grade 3-4 AST or ALT	
 Hold sotorasib dosing until recovery to Grade 1 or resolution Resume sotorasib dosing at the next lower dose level
AST or ALT > 3 x ULN with total bilirubin > 2 x ULN in the absence of alternative causes	
 Permanently discontinue sotorasib
Interstitial Lung Disease (ILD) or pneumonitis, any grade	
 Hold sotorasib dosing if either is suspected Permanently discontinue sotorasib dosing if either is confirmed
Grade 3 nausea or Grade 3-4 vomiting despite appropriate supportive care (including anti-emetic therapy)	
 Hold sotorasib dosing until recovery to Grade 1 or resolution Resume sotorasib dosing at the next lower dose level

8 CONCOMITANT THERAPY

8.1 PERMITTED MEDICATIONS

All medications (prescription and non-prescription/OTC) and blood products taken within 14 days of Cycle 1 Day 1 until the EOT visit will be recorded. The reason(s) for treatment, dose, and dates of treatment will be recorded. In addition, concomitant medications used to treat AEs occurring up to 30 days after the last dose of tarloxotinib will be recorded.

8.2 PROHIBITED MEDICATIONS

Concomitant medications and therapies excluded during the conduct of this trial include:

- Any other anticancer treatment including non-palliative radiation, chemotherapy, monoclonal antibodies, or TKIs

- Hormonal therapy for cancer
Note: Female patients who have been on hormone replacement therapy for menopausal symptoms for a period of at least 2 months will not be excluded from the study provided the planned hormone replacement therapy regimen remains largely unchanged during the conduct of the study
- Other tumor-targeted therapies
- Limited-field palliative radiotherapy to non-target lesions and bone-targeted agents, such as zoledronic acid and denosumab, are permitted.
- Tarloxotinib should be delayed during radiotherapy and resumed upon completion of radiotherapy, if deemed appropriate by the treating physician after discussion with the Medical Monitor.
- Medications that prolong QT interval and have a risk of Torsades de Pointes.
- Acid-Reducing Agents – avoid coadministration with proton pump inhibitors (PPI) and H2 receptor antagonists. If an acid-reducing agent cannot be avoided, adjust administration of sotorasib to be 4 hours before or 10 hours after a local antacid.
- Strong CYP3A4 Inducers: Avoid coadministration with strong CYP3A4 inducers
- CYP3A4 Substrates: Avoid coadministration with CYP3A4 substrates for which minimal concentration changes may lead to therapeutic failures of the substrate. If coadministration cannot be avoided, adjust the substrate dosage in accordance to its prescribing Information.
- P-gp substrates: Avoid coadministration with P-gp substrates for which minimal concentration changes may lead to serious toxicities. If coadministration cannot be avoided, decrease the substrate dosage in accordance with its Prescribing Information.

9 STUDY ASSESSMENTS

9.1 GENERAL GUIDELINES

Prior to any study specific activities, the subject must be aware of the nature of his/her disease and willingly consent to the study after being informed of study procedures, the experimental therapy, possible alternatives, risks and potential benefits.

9.2 STUDY CALENDAR

SCHEDULE OF EVENTS ⁸	SCR	C1 D1	C1 D8	C1 D15	C1 D22	C2 D1	C2 D8	C2 D15	C2 D22	C3+ D1	C3+ D8	C3+ D15	C3+ D22	EOT ⁹	SFU ⁶	LTFU
Informed consent	X															
Eligibility review	X															
Medical History	X															
Physical Exam	X	X				X				X				X	X	
ECOG Performance Status	X	X				X				X				X	X	
Vital signs ⁹	X													X	X	
Pre-infusion 30, 60, and 90 mins after EOI		X	X	X	X	X	X	X	X	X	X	X	X			
ECG 12-lead	X													X	X	
Pre-infusion EOI		X	X	X	X	X	X	X	X	X	X	X	X			
1h after EOI ¹¹		X	X	X	X	X	X	X	X	X	X	X	X			
2h after EOI ¹¹		X	X	X	X	X	X	X	X	X	X	X	X			
3h after EOI ¹¹		X	X	X	X	X	X	X	X	X	X	X	X			
4h after EOI ¹¹		X	X	X	X	X	X	X	X	X	X	X	X			
CBCD	X	X				X				X				X	X	
CMP ¹⁰	X	X	X	X	X	X	X	X	X	X	X	X	X	X	X	
Magnesium	X	X	X	X	X	X	X	X	X	X	X	X	X	X	X	
Phosphorous	X	X	X	X	X	X	X	X	X	X	X	X	X	X	X	
Serum potassium																
EOI		X				X										
3h post EOI		X				X										
Urinalysis	X															
B-HCG ²	X	X				X								X		
Biomarker samples/ctDNA samples ³		X				X								X		
Potassium Supplementation ⁴		X	X	X	X	X	X	X	X	X	X	X	X			
Tarloxotinib infusion	X	X	X	X	X	X	X	X	X	X	X	X	X			
Sotorasib dosing																
Tumor Assessment ⁵	X															
Concomitant Meds																
Adverse Events Assessment																
Survival status																X

Continuous dosing

*** Every 8 weeks (+/- 5 days) from Cycle 1 Day 1***

Every visit

Every visit

CT = Computed tomography, ECOG = Eastern Cooperative Oncology Group, EOI = End of Infusion, EOT = End of Treatment, SFU = Safety Follow-up, MRI = Magnetic Resonance Imaging, PET= Positron Emissions Tomography, QTcF = Corrected QT interval as calculated according to Fridericia's formula, SCR = Screening period

¹ For patients with Grade 3 QTcF prolongation (≥ 501 msec or > 60 msec increase compared to pre-infusion), repeat ECG every 15 to 30 mins until resolved to Grade 2 (481 to 500 msec) or lower (≤ 480 msec) and then obtain ECGs every hour up to 4 hours post infusion, or longer as clinically indicated.

² Serum pregnancy test at baseline, then urine pregnancy test, for women of childbearing potential

³ Collect blood for biomarkers per correlates manual.

⁴ If required. See section 7, potassium supplementation.

⁵ Perform radiographic assessments according to institutional practice. Include CT or MRI of the chest and abdomen, and if applicable, brain CT or MRI, bone scan, or PET-CT at screening. The baseline tumor assessment is required within 28 days prior to first dose of tarloxotinib. PET-CT may be substituted for a contrasted CT of the chest and abdomen if tumor measurements are obtained per RECIST 1.1 criteria. The same imaging modality used for baseline imaging must be used for subsequent tumor assessments in each patient.

⁶The EOT visit should be conducted within +/- 7 days of the last dose of tarloxotinib, and the safety follow-up should occur 30 days (+/- 7 days after the last dose of tarloxotinib).

⁷Patients may be followed for survival status every 3 months for up to 6 months after the last patient on study visit (LPV) at the investigator's discretion.

⁸Informed consent, medical history and physical exam/ECOG status to be obtained within 28 days of Cycle 1 Day 1. Baseline labs and ECG are to be obtained within 14 days of Cycle 1 Day 1.

⁹ Vital signs should include: Height (at screening only), weight, blood pressure, temperature, respirations, and O₂ saturation.

¹⁰ Liver function testing to be performed every 3 weeks for the first 3 months, then monthly as clinically indicated.

Cycles are 28 days in length. Study visits have a +/- 1 day window to allow for holidays or other rescheduling reasons, to be documented in the research record.

9.3 CRITERIA FOR REMOVAL FROM PROTOCOL TREATMENT

Subjects may discontinue study treatment at any time. Any subject who discontinues treatment will be asked to return to the study center to undergo end of treatment assessments as outlined within Study Calendar (Section 7.2). The primary reason for discontinuation should be recorded. In the absence of treatment delays due to adverse events, treatment may continue until one of the following criteria applies:

- Radiographic disease progression
- Clinical disease progression

- Inter-current illness that would, in the judgment of the investigator, affect assessments of clinical status to a significant degree or require discontinuation of study drugs
- Completion of protocol treatment.
- Unacceptable toxicity
- Death
- Subject may withdraw from the study at any time for any reason.
- Treatment delay for unacceptable duration for any toxicity in the opinion of the investigator
- Concomitant treatment with a prohibited medication
- Subject non-compliance

9.4 DURATION OF FOLLOW UP

Subjects may be followed for survival status every 3 months for up to 6 months after the last patient on study visit (LPV) at the investigator's discretion.

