2.2 SECONDARY OBJECTIVES

Objectives	Endpoints
To evaluate other measures of efficacy of the combination of tarloxotinib with sotorasib in patient with KRAS G12C mutated advanced NSCLC	
 - Duration of response (DOR) as measured from the date of first response to date of disease progression or death - Disease control rate (DCR) based on patient who had CR or PR or Stable disease (SD) for at least 2 cycles (8 weeks) - Best overall response (BOR) - Progression free survival (PFS) as measured from the date of first study drug dose to the date of the first objective documentation of radiographic disease progression or death due to any cause - Overall survival (OS) as measured from the date of first study drug dose to the date of death by any cause

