11 STATISTICAL CONSIDERATIONS

11.1 STUDY DESIGN

Study CTO # 103048 is a potentially multicenter, non-randomized, single cohort phase IB trial evaluating the safety and efficacy of tarloxotinib in combination with sotorasib in NSCLC patients with KRAS G12C mutation who have progressed on any small molecule KRAS G12C inhibitor.

Safety lead-in

A minimum of 6 patients and as many as 18 patients will be enrolled in a safety lead-in cohort to evaluate the safety of the combination of tarloxotinib and sotorasib. Sotorasib will be held at a fixed dose of 960 mg QD (the approved dose) while the starting dose of tarloxotinib will be the monotherapy RP2D equal to 150mg/m² QW (dose level 1 [DL1]). Following a 3+3 algorithm, an initial 3 patients will be enrolled at DL1. If 0 or 1 of 3 patients experience a DLT, an additional 3 patients will be enrolled to DL1. DL1 will be declared the combination RP2D (RP2D_c) if at most 1 of 6 patients treated at DL1 experience a DLT. Alternatively, if there are 2 or more DLTs observed at DL1, 3 patients will be enrolled at DL -1 and the 3+3 rules repeated for safety evaluation. The RP2D_c will be the highest DL at which at most 1 patient of 6 experiences a DLT. If DL -2 is considered too toxic, additional dose levels below DL -2 to be determined may be considered for safety.

Dose expansion

Once the tarloxotinib RP2D_c is reached, an expansion cohort of up to 12 patients will be enrolled to evaluate the safety of the combination of tarloxotinib and sotorasib. Eligible safety lead-in patients treated at the RP2D_c will be included in the expansion cohort.

The combination of tarloxotinib and sotorasib will not be considered promising if there is weak evidence the true objective response rate (ORR) exceeds 20%. Specifically, the trial will be declared negative if $\text{Prob}(\text{true ORR} > 20\% | \text{observed no. of responses}) < 20\%$, equivalent to observing at most 1 response in 12 patients. We assume the true ORR follows a beta (0.5, 0.5) prior distribution and, conditional on the true ORR, the number of responses follows a binomial distribution. If at least 2 responses in 12 patients are observed, the combination may be considered promising. Given 1 response in 12 patients, the probability the true ORR exceeds 20% is approximately 16%. Given 2 responses in 12 patients, the probability the true ORR exceeds 20% is approximately 42%.

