Overall survival (OS) is defined as the time from the date of start of treatment to the date of death due to any cause. OS will be summarized graphically using Kaplan-Meier curves. Median OS and corresponding 95% CI will be reported. For patients who are alive, lost to follow-up, or withdrawn from the study at the time of analysis, OS will be censored at the last date the patient is known to be alive.

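### Overall survival is a reported secondary endpoint, but survival follow-up after the safety visit is optional, so censoring can depend on prognosis

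*Combined protocol and SAP*

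**What the plan says.** Section 2.2 lists the endpoint: "Overall survival (OS) as measured from the date of first study drug dose to the date of death by any cause". Section 10.2 repeats it. Section 11.2.3 plans a Kaplan-Meier curve and adds: "Median OS and corresponding 95% CI will be reported".

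Survival status after treatment is covered in two places. Section 9.4 says: "Subjects may be followed for survival status every 3 months for up to 6 months after the last patient on study visit (LPV". The same sentence ends by leaving this to the investigator: "after the last patient on study visit (LPV) at the investigator's discretion". Footnote 7 of the study calendar (Section 9.2) is equally permissive. The calendar has a survival-status entry in its long-term follow-up column, but no text makes it compulsory. Neither place says how the discretion is to be used.

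The last scheduled contact before that stage is in calendar footnote 6: "the safety follow-up should occur 30 days (+/- 7 days after the last dose of tarloxotinib". Adverse-event reporting ends 28 days after the last dose (Section 11.2.4).

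The censoring rule in Section 11.2.3 treats all patients without a recorded death alike: "For patients who are alive, lost to follow-up, or withdrawn from the study at the time of analysis, OS will be censored". The date is set by the words "OS will be censored at the last date the patient is known to be alive".

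**The concern.** The plan commits to an OS estimate without requiring the data for it. Kaplan-Meier is valid only if a patient censored at time t has the same later risk of death as patients still under observation at t. Optional follow-up does not secure this, in two ways.

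- **Per patient.** If the investigator decides case by case, patients who are sicker, or those doing well elsewhere, may be followed less.
- **Whole study.** If the investigator decides once not to run long-term follow-up, censoring falls about a month after treatment stops. Most of the removal criteria in Section 9.3 (radiographic or clinical progression, toxicity, intercurrent illness) are related to prognosis.

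Section 11.2.3 has no minimum follow-up, no requirement to establish vital status before analysis, and no look at why patients were censored. What is at stake is the reported OS curve and median. To a lesser extent PFS and DOR are affected too, since death is an event in both and a death after the safety visit could be missed.

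**Working it through.** **No figure to reproduce.** The documents state no expected median, event count or power for OS. Only these inputs come from them: the safety visit 30 days after the last tarloxotinib dose, the end of follow-up at up to 6 months after the last patient's visit, and the cohort size (Section 11.1: "an expansion cohort of up to 12 patients will be enrolled", counting eligible lead-in patients). Everything else below is assumed.

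**Estimator.** S(t) is the product over death times of (1 − deaths / number at risk). The median is the first t with S(t) ≤ 0.5.

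**Check 1: selective follow-up, large sample.** Assumptions:
- OS is exponential with median 8 months (rate ln 2 / 8 = 0.087 per month).
- Time on treatment is exponential with median 3 months (rate ln 2 / 3 = 0.231), independent of OS but ended by death.
- Administrative censoring is uniform over 9 to 24 months.
- An unfollowed patient is censored 1 month after stopping treatment.
- In the selective cases, 50% of one group and 10% of the other are not followed.

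The result depends on how the near-death group is defined:

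| Near-death group | Near-death group followed less | Longer survivors followed less |
|---|---|---|
| Death within 3 months of stopping treatment | 8.6 | 7.3 |
| Death before month 8 | 9.3 | 6.9 |
| Remaining survival below its median | 9.5 | 7.1 |

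Complete follow-up gives 8.0, and so does leaving a random 30% unfollowed. The span is about 7 to 9.5 months. Among patients alive at the safety visit, 16% to 44% are unfollowed, depending on the cell.

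**Check 2: nobody followed after the safety visit, large sample.** With treatment duration independent of OS as above, this still gives 8.0, so lack of follow-up alone does no harm. Now let the two share a gamma frailty of mean 1 and variance 0.5. Then S(t) = (1 + 0.5λt)^−2, and a median of 8 needs λ = (√2 − 1) / (0.5 × 8) = 0.104 per month. The median becomes 9.9 months if treatment ends at 1.5 times the death rate, and 11.8 if median time on treatment is 3 months: about 11. Following a random half gives 8.6 and 8.8.

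**Check 3: 12 patients.** Assumptions are uniform accrual over 18 months, the same frailty, treatment ending at 1.5 times the death rate, and cut-off 6 months after the last patient's visit. For an assumed true median of 9 months:

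| Follow-up after safety visit | Typical KM median | Mean deaths captured, of 12 |
|---|---|---|
| All patients | 7.8 | 10.4 |
| Worse-prognosis half only | 8.4 | 8.3 |
| Random half | 9.5 | 7.9 |
| Better-prognosis half only | 11.3 | 7.5 |
| Nobody | 11.5 | 5.4 |

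Relative to following all, the two selective rules give 8.4/7.8 = +8% and 11.3/7.8 = +45%. For true medians of 6 and 12 months the same rules give +6% and +36%, and +8% and +41%. Part of these shifts is small-sample behaviour of the median: following all gives 7.8, below the true 9.

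**Yardstick.** In the Check 1 model with complete follow-up and 12 patients, the 95% sampling range of the KM median is about 2.7 to 17 months.

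**The case against.** The strongest reply is that little depends on OS. It is secondary and descriptive, with no comparator or hypothesis. The promising/not-promising rule in Section 11.1 uses response only, and the pause rule in Section 11.3 uses toxicity only. With 12 patients the sampling range above exceeds any shift computed here. This stands, and it limits the weight of the point. It does not remove it: imprecision shows in the confidence interval, whereas informative censoring does not.

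Four stronger readings are tempting, and the documents do not support them.

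- **Unfollowed patients are always censored at the end of treatment.** The date last known alive may come from any source, and Sections 5.1 and 5.1.2 recruit largely from the centre's own clinics, so routine records may supply later dates. External referrals and possible sub-sites make this less reliable.
- **The investigator will pick patients by prognosis.** The wording fits a single study-level decision equally well. Check 2 shows that this reading can also bias OS, but only if time on treatment and survival are related.
- **The bias has a known size or direction.** Check 1 gives shifts both ways. With shared prognosis (Checks 2 and 3) they are upward. All rest on assumptions.
- **The problem could not be found or repaired.** Listing reasons for censoring would reveal it, and a vital-status sweep before analysis could largely repair it. The plan simply requires neither.

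**Conclusion.** The point holds in a limited form. Survival follow-up is optional in both places that describe it, while a Kaplan-Meier median OS is promised, and nothing in the plan prevents or checks for prognosis-related censoring. The documents show that bias is possible, not that it will occur.

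As an illustration only, for an assumed true median of 8 months, the large-sample estimate runs from about 7 to 9.5 months under selective follow-up. It is about 11 (10 to 12 in the two settings tried) if nobody is followed and treatment duration shares prognosis with survival. In the 12-patient illustrations, captured deaths fall from about 10–11 to about 7–8.5 under selective follow-up.

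The consequence is confined to reported OS and to deaths entering PFS and DOR. A reader might infer that the trial's conclusion on efficacy is compromised. It is not, because that rule does not use OS.

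**What to change.** 1. In Section 9.4 and calendar footnote 7, replace the permissive, discretionary wording with a requirement: *every treated patient will have survival status obtained every 3 months, by telephone or chart review, until death, withdrawal of consent, or 6 months after the last patient's on-study visit.* The interval and end point stay as they are. OS is analysed in the efficacy set, but following all treated patients avoids deciding membership of that set first.
2. In Section 11.2.3, require vital status to be established for every patient before the OS analysis, and list each censored patient with the date and reason.

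The cost is a few calls or chart checks per patient, for roughly 12 to 18 patients, with no added visits or procedures. It should be done while the trial is running, since later retrieval from records may be incomplete.
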